11.5 Table3.OARdoseparameters to be recorded

Brainstem	Maximum Dose _____
SpinalCord	Maximum Dose _____
RightParotid	Mean Dose _____
	V_{30Gy} _____
LeftParotid	Mean Dose _____
	V_{30Gy} _____
Parotids(bilateral)	D20cc _____
SubmandibularGland	Mean Dose _____
ExtendedOralCavity	Maximum Dose _____
	Mean Dose _____
Lips	Maximum Dose _____
	Mean Dose _____
BuccalMucosa	Maximum Dose _____
	Mean Dose _____
Mandible	Maximum Dose _____
PharyngealConstrictors	Mean Dose _____

11.6 FACT-G(Version4)

Below is a list of statements that other people with your illness have said are important. **Please circle or mark on number per line to indicate your response as it applies to the past 7 days.**

PHYSICAL WELL-BEING		Not at all	A little bit	Some- what	Quite abit	Very much
GP1	I have a lack of energy	0	1	2	3	4
GP2	I have nausea	0	1	2	3	4
GP3	Because of my physical condition, I have trouble meeting the needs of my family	0	1	2	3	4
GP4	I have pain	0	1	2	3	4
GP5	I am bothered by side effects of treatment	0	1	2	3	4
GP6	I feel ill	0	1	2	3	4
GP7	I am forced to spend time in bed	0	1	2	3	4
SOCIAL/FAMILY WELL-BEING		Not at all	A little bit	Some- what	Quite abit	Very much
GS1	I feel close to my friends	0	1	2	3	4
GS2	I get emotional support from my family	0	1	2	3	4
GS3	I get support from my friends	0	1	2	3	4
GS4	My family has accepted my illness	0	1	2	3	4
GS5	I am satisfied with family communication about my illness	0	1	2	3	4
GS6	I feel close to my partner (or the person who is my main support)	0	1	2	3	4
Q1	
Regardless of your current level of sexual activity, please answer the following question. If you prefer not to answer it, please mark this box  and go to the next section.
					
GS7	I am satisfied with my sex life	0	1	2	3	4

FACT-G(Version4)

Please circle or mark on a number per line to indicate your response as it applies to the past 7 days.

EMOTIONAL WELL-BEING

		Not at all	A little bit	Some-what	Quite a bit	Very much
GE1	I feel sad	0	1	2	3	4
GE2	I am satisfied with how I am coping with my illness.....	0	1	2	3	4
GE3	I am losing hope in the fight against my illness.....	0	1	2	3	4
GE4	I feel nervous.....	0	1	2	3	4
GES	I worry about dying	0	1	2	3	4
GE6	I worry that my condition will get worse	0	1	2	3	4

FUNCTIONAL WELL-BEING

		Not at all	A little bit	Some-what	Quite a bit	Very much
GF1	I am able to work (include work at home)	0	1	2	3	4
GF2	My work (include work at home) is fulfilling.....	0	1	2	3	4
GF3	I am able to enjoy life.....	0	1	2	3	4
GF4	I have accepted my illness.....	0	1	2	3	4
GF5	I am sleeping well	0	1	2	3	4
GF6	I am enjoying the things I usually do for fun	0	1	2	3	4
GF7	I am content with the quality of my life right now.....	0	1	2	3	4

11.7 FACT-H&N(Version4)

Please circle or mark one number per line to indicate your response as it applies to the past 7 days.

ADDITIONAL CONCERNS		Not at all	A little bit	Some-what	Quite a bit	Very much
H&N1	I am able to eat the foods that I like	0	1	2	3	4
H&N2	My mouth is dry	0	1	2	3	4
H&N3	I have trouble breathing	0	1	2	3	4
H&N4	My voice has its usual quality and strength	0	1	2	3	4
H&N5	I am able to eat as much food as I want	0	1	2	3	4
H&N6	I am unhappy with how my face and neck look.....	0	1	2	3	4
H&N7	I can swallow naturally and easily	0	1	2	3	4
H&N8	I smoke cigarettes or other tobacco products	0	1	2	3	4
H&N9	I drink alcohol (e.g. beer, wine, etc.).....	0	1	2	3	4
H&N 10	I am able to communicate with others	0	1	2	3	4
H&N 11	I can eat solid foods.....	0	1	2	3	4
H&N 12	I have pain in my mouth, throat or neck	0	1	2	3	4

11.8 OralMucositisDailyQuestionnaire

2. During the PAST 24 HOURS how much MOUTH AND THROAT SORENESS DID YOU HAVE? (Circle one number)

0 No soreness	1 A little soreness	2 Moderate soreness	3 Quite a lot of soreness	4 Extreme soreness
------------------	------------------------	------------------------	---------------------------------	-----------------------

3. During the PAST 24 HOURS how much did MOUTH AND THROAT SORENESS limit you in each of the following activities:

	Not limited	Limited a little	Limited some	Limited a lot	Unable to do
a. Swallowing	0	1	2	3	4
b. Drinking	0	1	2	3	4
c. Eating	0	1	2	3	4
d. Talking	0	1	2	3	4
e. Sleeping	0	1	2	3	4

4. On a scale of 0 to 10, how would you rate your OVERALL MOUTH AND THROAT SORENESS during the PAST 24 HOURS? (Please circle the most appropriate number)

0 None	1	2	3	4	5	6	7	8	9	10 Worst possible
-----------	---	---	---	---	---	---	---	---	---	-------------------------

*Questions 2 through 4 of OMDQ adapted from Elting et al, 2008 [27]

11.9 Data and Safety Monitoring Report

Barbara Ann KARMANOS Cancer Institute: Protocol Specific Data and Safety Monitoring Report

PROTOCOL #: _____

REPORT DATE: _____

PROTOCOL TITLE					
ATTENDANCE					
PROTOCOL ACTIVITY SINCE LAST REPORT					
Accrual Goal:	Eligible:		Total number of AE's to date:		
Accrual to Date:	Ineligible (provide reason):				
Accrual Since Last Monthly Report:					
Specifically for Phase I Trial &/or Dose Escalating Trials:					
Dose Level	Accrual				
1					
2					
3					
Record all Grade 3, 4, and 5 Adverse Events (AE). Group by category of AE. record the date OF the occurrence, attribution and if reportable to the IRB. Shade the rows of the AE's that have occurred for this Report. attach the HIC UP report form for these reportable events that occurred on this report.					
Pt. ID#	Category and type of adverse reaction	Date of Occurrence	Grade ¹	Attribution ²	Reportable to IRB (Y/N) Yes with date

1. Grade: 1-Mild, 2-Moderate, 3- Severe, 4-Life-threatening, or 5- Death.

2. Attribution: 1-unrelated, 2 - unlikely, 3 - possibly, 4 - probably, or 5 - definitely

OFF TREATMENT ~ Provide reason [progression, death, toxicity, completed therapy, etc].	
PROTOCOL VIOLATIONS Deviations from protocol treatment, monitoring, or study calendar.	
PROTOCOL AMENDMENTS Include date submitted to regulatory bodies and date approved.	

OTHER COMMENTS			
Investigator Signature:		Data Manager Signature:	

11.10 StudyCalendar

	Treatment (low-level laser therapy)					Follow Up (low-level laser therapy)	
	Pre-Study		Treatment Period		Last Day of Treatment	Follow Up Period	
	Screening -28 to -1	Baseline Day 0	Weekly Visit	Visits 3x/week	Last Day of Treatment	Follow Up Week 2	Follow Up Month 3
Medical History	X						
Demographics	X						
Physical Exam	X						
Assessment of Oral Mucositis (WHO)		X	X		X	X	X
Chemotherapy [1; AN]					X		
Organs at Risk Review (OAR) [2; AN]					X		
Radiation Therapy [3; AN]					X		
Dietary Assessment		X	X		X	X	X
Mouth Pain, Throat Pain, PEG Tube, Alcohol use, Smoking, Weight		X	X		X	X	X
FACT-G		X	X		X	X	X
Oral Mucositis Daily Questionnaire		X	X		X	X	X
FACT-H&N		X	X		X	X	X
Low-level Laser Therapy (LLLT) Treatment Record Form			X	X			
Trismus Assessment		X			X	X	X
Adverse Events: CTCAE (oral mucositis, dysphagia, xerostomia, dysgeusia, and dermatitis)		X	X		X	X	X
Concomitant Medications (for analgesia & mucositis)		X	X		X	X	X

Calendar Foot Notes

1. The prescribed course of chemotherapy will be determined by the managing medical oncologist per institutional practices and will not be altered based on this study.
2. Dose limits to OARs will be determined by institutional practice and specific dose-constraints will not be required on this protocol.
3. Radiation therapy will be delivered with an intensity modulated radiation therapy (IMRT) technique and/or image-guided radiation therapy (IGRT). The prescribed course of radiotherapy will not be altered based on this study. Radiotherapy will be delivered 5 days per week, Monday - Friday with one radiation treatment given per day. The planned cumulative dose of radiation will be determined by the treating physician and will range from 5000 - 7000 cGy in 180 - 200 cGy daily fractions over the course of 5-7 weeks. This treatment is not part of the research protocol.

AN. As Needed

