2. During the PAST 24 HOURS how much MOUTH AND THROAT SORENESS DID YOU HAVE? (Circle one number)

0 No soreness	1 A little soreness	2 Moderate soreness	3 Quite a lot of soreness	4 Extreme soreness
------------------	------------------------	------------------------	------------------------------	-----------------------

3. During the PAST 24 HOURS how much did MOUTH AND THROAT SORENESS limit you in each of the following activities:

a. Swallowing	Not limited 0	Limited a little 1	Limited some 2	Limited a lot 3	Unable to do 4
---------------	------------------	-----------------------	-------------------	--------------------	-------------------

b. Drinking	0	1	2	3	4
c. Eating	0	1	2	3	4
d. Talking	0	1	2	3	4
e. Sleeping	0	1	2	3	4

4. On a scale of 0 to 10, how would you rate your OVERALL MOUTH AND THROAT SORENESS during the PAST 24 HOURS? (Please circle the most appropriate number)

*Questions 2 through 4 of OMDQ adapted from Elting et al, 2008 [27]

Dysphagia will be assessed using the NCI CTCAE version 4.0 [25] as follows:

Adverse Event	Grade				
	1	2	3	4	5
Dysphagia	Symptomatic, able to eat regular diet	Symptomatic and altered eating/swallowing	Severely altered eating/swallowing; tube feeding or TPN or hospitalization indicated	Life-threatening consequences; urgent intervention indicated	Death

Xerostomia will be assessed using the NCI CTCAE version 4.0 [25] as follows:

Adverse Event	Grade				
	1	2	3	4	5
Dry Mouth	Symptomatic (e.g., dry or thick saliva) without significant dietary alteration; unstimulated saliva flow >0.2 ml/min	Moderate symptoms; oral intake alterations (e.g., copious water, other lubricants, diet limited to purees and/or soft, moist foods); unstimulated saliva 0.1 to 0.2 ml/min	Inability to adequately aliment orally; tube feeding or TPN indicated; unstimulated saliva	-	-

Dysgeusia will be assessed using the NCI CTCAE version 4.0 [25] as follows:

Adverse Event	Grade				
	1	2	3	4	5
Dysgeusia	Altered taste but no change in diet	Altered taste with change in diet (e.g., oral supplements); noxious or unpleasant taste; loss of taste	-	-	-

Dermatitis will be assessed using the NCI CTCAE version 4.0 [25] as follows:

Adverse Event	Grade				
	1	2	3	4	5
Dermatitis radiation	Faint erythema or dry desquamation	Moderate to brisk erythema; patchy moist desquamation, mostly confined to	Moist desquamation in areas other than skin folds and	Life-threatening consequences; skin necrosis or ulceration of full	Death

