6.7 Specific Toxic Outcomes

No toxicities or dose-limiting toxicities have been reported in association with LLLT in the biomedical literature. Specifically with respect to LLLT for the prevention and/or management of oral mucositis, no toxicities or DLTs have been reported. Any toxicities arising would be anticipated to be localized to the exposed tissues. These would include undesignated skin/mucosal changes, such as localized skin erythema, mucosal swelling (not typically associated with mucositis) or unanticipated sensory changes. Of note, oral mucositis may develop despite LLLT and will not be considered a treatment-related toxicity.

We will closely monitor the following outcomes: grade 3 oral dysesthesia (burning/tingling sensation in the distribution exposed to LLLT), grade 3 or 4 oral mucosal swelling not attributable to mucositis (GI Disorders, other, specify), Grade 3 erythema and/or pain of the skin (in the distribution exposed to LLLT), visual loss, blurred vision, retinal tear or detachment, uveitis, or other eye disorders. If 2 or more patients out of the first 10 (or fewer) treated in the phase II portion of the study develop a grade III (using the CTCAE guidelines) or higher toxicity in any of these categories that are probably or definitely related to the LLLT treatment received within the first 2 weeks after the completion of treatment, we would recommend revisiting the study for safety reasons. Adjudication is necessary to ensure that we judge this study based on adverse events that are specific to LLLT therapy and not any other therapy that the patient happens to receive. We will continue to monitor these specific toxic outcomes throughout the course of the trial, in a sliding window fashion.

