7.2 AdverseEventCharacteristics

The occurrence of adverse events should be sought by non-directive questioning of the patient at each visit during the study. Adverse events also may be detected when they are volunteered by the patient during or between visits or through physical examination, laboratory test, or other assessments. As far as possible, each adverse event should be evaluated to determine:

1. The severity grade (CTCAE grade 1-4)
2. Its relationship to each study treatment (suspected/not suspected)
3. Its duration (start and end dates or if continuing at final exam)
4. Action taken (no action taken/temporarily interrupted; study treatment permanently discontinued due to this adverse event; concomitant medication taken; non-drug therapy given; hospitalization/prolonged hospitalization)
5. Whether it is serious, where a serious adverse event (SAE) is defined as one which:
 - Is fatal or life-threatening
 - Results in persistent or significant disability/incapacity
 - Constitutes a congenital anomaly/birth defect
 - Requires inpatient hospitalization or prolongation of existing hospitalization, unless hospitalization is for:
 - Routine treatment or monitoring of the studied indication, not associated with any deterioration in condition (specify what this includes)

- Elective or pre-planned treatment for a pre-existing condition that is unrelated to the indication under study and has not worsened since signing the informed consent
- Treatment on an emergency outpatient basis for an event not fulfilling any of the definitions of a SAE given above and not resulting in hospital admission
- Social reasons and respite care in the absence of any deterioration in the patient's general condition
- Is medically significant, i.e., defined as an event that jeopardizes the patient or may require medical or surgical intervention to prevent one of the outcomes listed above

Unlike routine safety assessments, SAEs are monitored continuously and have special reporting requirements; see protocol section on Serious Adverse Event reporting.

All adverse events should be treated appropriately. Once an adverse event is detected, it should be followed until its resolution, an assessment should be made at each visit (or more frequently, if necessary) of any changes in its severity, its suspected relationship to the study treatment, any of the interventions required to treat it, and its outcome.

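### Most outcomes that feed the section 6.7 safety trigger have no directed item on the weekly toxicity sheet or in the calendar's CTCAE row; skin is covered only as radiation dermatitis

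*Combined protocol and SAP*

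**What the plan says.** Section 6.7 lists the outcomes of special interest for the laser. It opens "We will closely monitor the following outcomes: grade 3 oral dysesthesia (burning/tingling sensation in the distribution exposed to LLLT", adds grade 3 or 4 swelling of the oral mucosa that is not mucositis, and continues "Grade 3 erythema and/or pain of the skin (in the distribution exposed to LLLT), visual loss, blurred vision, retinal tear or detachment, uveitis", closing with other eye disorders. The rule follows: "If 2 or more patients out of the first 10 (or fewer) treated in the phase II portion of the study develop a grade III" or higher toxicity in any of these categories, the investigators would recommend revisiting the study. To count, an event must be "probably or definitely related to the LLLT treatment received within the first 2 weeks after the completion of treatment". Monitoring then continues in a sliding window.

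The calendar (11.10) has one CTCAE row, "Adverse Events: CTCAE (oral mucositis, dysphagia, xerostomia, dysgeusia, and dermatitis", marked at baseline, weekly, the last treatment day, week 2 and month 3. The Weekly Toxicity Scoring Sheet (11.2) carries scales for those five terms, the WHO mucositis grade, 0-10 mouth and throat pain, diet, weight, analgesics, feeding tube, smoking and alcohol.

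For adverse events in general, 7.2 states: "The occurrence of adverse events should be sought by non-directive questioning of the patient at each visit during the study". It adds volunteered reports, physical examination and other assessments as further routes. Section 7.1 provides an Adverse Events CRF and a five-level attribution scale, and the monitoring report in 11.9 logs all grade 3 to 5 events with attribution.

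**The concern.** Section 6.7 promises close monitoring of a short, named list, but the form completed every week asks about a different list. The two meet only at radiation dermatitis. These patients are on chemoradiation: they already have mouth pain and skin redness, and 7.2 lists numbness of the fingers and toes among the background effects. Oral tingling or blurred vision could go unmentioned, or be attributed to mucositis or chemotherapy.

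Two features raise the stakes. Section 6.6 says the weekly toxicity data are collected to check the claim that LLLT adds no specific toxicity, and a count of zero from forms that do not ask is weak support for that claim. Section 6.8 also excludes the 6.7 outcomes from its stopping table, so that boundary is not designed to count them.

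**Working it through.** **Step 1. Set the trigger list against the forms.**

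| 6.7 outcome | Weekly sheet (11.2) | CTCAE row (11.10) | Other routes |
|---|---|---|---|
| Oral dysesthesia | No item; mouth pain 0-10 only | Not named | Open questioning (7.2); the OMDQ asks about soreness, not tingling |
| Mucosal swelling, not mucositis | No item | Not named | Oral exam at each LLLT session (4.3), done to find mucositis |
| Erythema of LLLT-field skin | Only as radiation dermatitis | Only as dermatitis | Open questioning, examination |
| Pain of LLLT-field skin | No item | Not named | Open questioning |
| Visual loss, blurred vision, other eye disorders | No item | Not named | Open questioning; no eye check scheduled |

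The LLLT Treatment Record Form (11.3) has columns for mucositis, treated area and settings plus free-text notes, with no adverse event field. The calendar's physical examination row is marked at screening only, although 5.1 has a physician see each patient at least weekly. Section 2.5 recognises an eye hazard for this laser class and requires eyewear, yet no form asks about the eyes, even at baseline.

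**Step 2. Check whether the skin item can be graded.** On the dermatitis scale in 5.2 and 11.2, grade 1 includes faint erythema and grade 2 begins "Moderate to brisk erythema; patchy moist desquamation, mostly confined to" skin folds and creases. Grade 3 is moist desquamation beyond the folds, or bleeding on minor trauma. Erythema alone therefore never reaches grade 3 on that scale. Section 7.1 has a mild-to-life-threatening fallback where CTCAE has no grading, but 6.7 does not say that the skin item uses it.

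**Step 3. Check attribution.** The trigger counts only probable or definite relation to LLLT. The weekly sheet has no attribution field. Section 7.2 asks for suspected or not suspected; 7.1 and 11.9 use five levels. Only the five-level scale maps onto the trigger.

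**Step 4. Ask what under-capture would do to the rule.** The plan states no operating characteristic for 2 of 10, so there is no figure to reproduce. Let p be the true rate of qualifying events per patient and s the probability that such an event is captured. Both are assumptions; the documents give neither. With q = p × s and 10 independent patients,

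P(2 or more of 10) = 1 − (1 − q)^10 − 10q(1 − q)^9.

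Example, p = 0.20:
- s = 1: q = 0.20, so 1 − 0.107 − 0.268 = 0.624 after rounding.
- s = 0.5: q = 0.10, so 1 − 0.349 − 0.387 = 0.264.

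| True rate p | s = 1 | s = 0.9 | s = 0.75 | s = 0.5 | s = 0.25 |
|---|---|---|---|---|---|
| 0.05 | 0.086 | 0.072 | 0.052 | 0.025 | 0.007 |
| 0.10 | 0.264 | 0.225 | 0.170 | 0.086 | 0.025 |
| 0.20 | 0.624 | 0.561 | 0.456 | 0.264 | 0.086 |
| 0.30 | 0.851 | 0.798 | 0.695 | 0.456 | 0.170 |

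The direction is certain: missed events make the trigger less likely to fire. The size runs from slight at 90% capture to large at 50% or below, and nothing in the documents says which applies. The table covers one group of 10 and ignores the later sliding window.

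**The case against.** The plan has a working system for adverse events, and the weekly sheet is not its only source. Staff must ask at every visit, and a physician sees each patient at least weekly. The mouth is examined at each LLLT session, three times a week, which gives a regular chance to see severe swelling. Any grade 3 to 5 event has a place on the Adverse Events CRF and in the monitoring log, with attribution, and the monitoring committee reviews the reports monthly. The trigger counts only events of grade 3 or higher that are probably or definitely related, and severe events are the ones open questioning is least likely to miss. Reaching 2 of 10 leads only to a recommendation to revisit the study.

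Most of this stands, and it rules out three stronger readings that a reader might draw.
- **That the count depends on patients volunteering symptoms.** Section 7.2 requires questioning at each visit and lists volunteered reports as an additional route.
- **That LLLT-field skin is not assessed, or that grade 3 erythema cannot be graded at all.** Erythema is graded weekly as radiation dermatitis, and a separate skin event could be graded with the 7.1 fallback.
- **That the trigger has lost a known share of its sensitivity.** The event rate and the capture rate are both assumed, and the protocol expects no LLLT toxicity.

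What the objection does not answer is that the CRF and the log store events already detected; they do not prompt for them. The oral exam is aimed at mucositis and cannot reveal blurred vision or tingling.

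**Conclusion.** The gap is real and narrow. Section 6.7 commits to close monitoring of named outcomes, but the weekly sheet and the calendar's CTCAE row have no directed item for the eye, dysesthesia or swelling outcomes. They cover skin only through a scale whose grade 3 is not defined by erythema, and the sheet has no item for LLLT-field skin pain and no attribution field. Ascertainment rests on open questioning, general examination and general event records, so visual or sensory events may be missed or merged into background toxicity. The loss cannot be sized from the documents; the probabilities above are illustrations under assumed rates. This is a weakness in form design that should be corrected, not a contradiction in the plan, and it does not touch the primary analysis.

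**What to change.** - Add prompted lines to the Weekly Toxicity Scoring Sheet (11.2) for oral dysesthesia, oral mucosal swelling not due to mucositis, erythema or pain of skin in the LLLT field, and visual symptoms or eye disorder. Give each a grade and the five-level attribution of 7.1.
- Name the same outcomes in the calendar's CTCAE row (11.10), from baseline through the 2-week follow-up, which matches the trigger's time window. The baseline entry separates pre-existing complaints from new ones.
- State in 6.7 which scale grades the LLLT-field skin item, for example the 7.1 fallback rather than radiation dermatitis.
- Leave the 2-of-10 threshold as the investigators set it.

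The cost is four lines on a sheet already used at baseline, weekly and follow-up visits, with no new visit, test or staff. The downside is that prompts will also bring in more low-grade, unrelated complaints; the grade and attribution entries keep these out of the trigger count.
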